- In consultation with Co-PI [name], a fellowship-trained urologic oncologist, and Co-I [name], an expert prostate cancer medical oncologist, and Co-I [name], Chief of Radiation Oncology at AAVA, we will provide multi-disciplinary review for questionable low-value ADT use.

- Clinic visits identified during chart reviews or multi-disciplinary review as involving proper justification for ADT use will not be considered appropriate for ADT de-implementation.

- When identifying clinic visits as appropriate for the ADT de-implementation interventions, no interventions will be triggered on any clinic visits for providers who opted out of the study.
- We will track numbers of identified low-value ADT injections each week per site.
- Paper records created for chart review purposes will be labeled with a study ID only and stored in locked filing cabinets in the locked 3rd floor CCMR suite in VA-rented space at NCRC. Once data is digitized, the paper copies will be placed in the VA's secure shredder bin.

PATIENT DASHBOARD IN CPRS

- See Appendix IV for screenshots of an example dashboard.
- We will work with [name], MBA, our consultant technology developer and study team member, to create a patient dashboard accessible through AAVA CPRS.
- The dashboard will enable the study team to:
 - View upcoming clinic visits identified as appropriate for ADT de-implementation.
 - Know when we can assign the progress note template to providers who have an upcoming clinic visit identified as appropriate for ADT de-implementation.
 - Determine when a patient has an order for ADT in CPRS.
 - Complete quality checks (e.g., to know which patient records to look at to confirm the order check was generated).
- Once a site is randomized, the Data Manager will run a new data pull for that site. She will create a file with the list of potentially eligible patients from CDW to upload to the dashboard. A separate Excel spreadsheet will be created for each site. The data files will be saved here: . Data files will be uploaded to the dashboard.
- Dashboard administrators will download export data files from the dashboard and save here: . These data will then be imported into the database. This will also need to be done when changes to the dashboard data fields are made, as the export fields need to match the database import fields.

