- Questionable cases will be subject to multi-disciplinary review during the weekly study team meeting:
 - Questionable bone metastases
 - Intermittent ADT
 - Other questionable cases
- All target ADT orders confirmed will be subject to the **Or** Intervention (see below).

PILOT TARGET CLINIC VISIT IDENTIFICATION (Sc)

- Every week, the study team will review the list of potentially eligible clinic visits for providers' clinic schedules the following Monday-Friday.
- Study staff will screen the list of clinic visits throughout the implementation period to identify target clinic visits for the **Sc** intervention.
- Questionable cases will be subject to multi-disciplinary review during the weekly study team meeting:
 - Questionable bone metastases
 - Intermittent ADT
 - Other questionable cases
- All target clinic visits confirmed will be subject to the **Sc** Intervention (see below).

IMPLEMENTATION EDUCATION SESSION (IES)

- Study staff will work with Site Champions to schedule a virtual IES.
- The IES will ideally be scheduled during Grand Rounds or another regularly scheduled meeting.
- The IES will be ~10 - 15 minutes and include a PowerPoint presentation (see attached).
 - The IES presentation will be tailored to each facility, as needed, and revised based on provider feedback
 - The Study PI plans to facilitate the IES, but it may also be conducted by study staff or designee chosen by site leadership at their request
- The purpose of the IES will be to explain the importance of the study, describe the light touch interventions, and encourage use of the tools provided with the interventions. We will also field questions and address any concerns from providers.

INSTRUCTIONS FOR SCHEDULING IES MEETINGS

NOTE: Be mindful of the different time zones when scheduling

- Request the meeting organizers send calendar invitations to the following email addresses:
 - Site Champion's email
 - [name] VA and UM emails
 - Living Well group email
- We will provide the meeting organizers a copy of the PPT upon request.
- Update site status in database with date and time of scheduled IES.
- Add IES meetings to the shared Living Well calendar.
- When IES's are scheduled by the study team, include the information below in the meeting invite:

Purpose

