- Once the CROC has been switched to live mode, study staff will place a "Living Well ADT" health factor in the EMR of patients whose clinic visits study staff have confirmed to be targets for ADT de-implementation. We will enter health factors as we identify eligible patients. This health factor combined with a low PSA level (most recent PSA < 2ng/mL) will trigger the ADT Order Check Attestation Intervention (**Or**) when the provider places an order for ADT (Lupron, Eligard, Viadur, Goserilin, and Zolodex).
- Providers may override the CROC by entering a number from the order check text that corresponds to the reason they are overriding the order check. Providers are also able to enter text if a numbered reason is not listed.
- If providers opt-out after the health factor was placed for one of their patients, study staff will remove the health factor in CPRS. For a provider who opts-out, the Study Data Manager will run a query in our Access tracking database to pull a list of his/her patients. The Study Team will not place a health factor in the EMR of patients whose provider has opted out.
- Study staff will do periodic quality control checks to ensure the intervention is working as expected and work with the site CAC's to make adjustments as necessary.
- Appropriate use of the indication will be tracked for fidelity. We will track comments entered by providers to override order checks. The Study Data Manager will periodically pull comments from order checks (there are data tables for order checks that contain text for open field that are stored in CDW).
 - Using a combination of progress notes and other CPRS data, study staff will check to determine whether the patient received the injection.
- Deimplementing Or – study staff will remove HFs for intervention patients. We'll ask site to remove study HF from their CPRS.

CPRS INSTRUCTIONS FOR OR INTERVENTION

OPENING CPRS

- Go to "VA Shortcuts" (star icon on desktop)
- Select "CPRS _Launcher" (rocket icon)
- Select: VISN 03 or VISN 22
- Select site: Ex - Manhattan, NY
- Launch CPRS button

PLACING A HEALTH FACTOR

While in a patient record in CPRS:

- Click on the "Notes" tab (bottom of screen)

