- 1) Dial study phone number (from jabber or any phone)
- 2) Once voicemail starts, select *
- 3) Instruction's state: "Enter your ID followed by pound" enter phone number: **xxxxx#**
- 4) Instruction's state: "Enter your pin followed by pound" enter pin: **xxxxx#**

(Note: PIN #'s are required to be changed often, study staff will add a 1 to pin each time it needs to be updated.

PILOT STUDY FLOW CHART

PILOT RANDOMIZED IMPLEMENTATION TRIAL

TRIAL SITE SELECTION

- We will update national VA and Medicare data to identify eligible sites for the cRCT.
- All VA sites with high rates of low-value ADT from 2020 – 2022 will be considered eligible to participate in the study.
- We will start with the 40 facilities with the highest rates of low-value ADT and continue down the list as necessary.
- We will exclude sites requiring translated materials (e.g., Puerto Rico).
- If feasible, we will exclude sites scheduled to transition to Cerner prior to the end of the cRCT.
- We will randomize 4 VA facilities with high rates of low-value ADT use.

TRIAL SITE RECRUITMENT & RANDOMIZATION

- The top 4 sites with high rates of low-value ADT use and meeting above criteria will be invited to participate in the study.
- All invited sites that agree to participate will be included.
- We expect 80% participation by eligible sites.
- If sites are unwilling or unable to participate, we will continue down the list of sites until we reach a maximum of 4 participating sites.
- Study staff will send an email from the study Co-PI to Urology Chiefs to recruit as Site Champions.
 - If we are unable to contact Urology Chiefs, or if we do not receive a response from the Urology Chief after two formal email contacts, we may reach out to the Chief of Surgery, Chief of Med/Onc, or Chief of Rad/Onc (and copy the ACOS/R) about serving as Site Champion.
 - If the Urology Chief declines to serve as Site Champion, we may ask if they have any suggestions for an alternate designee.
 - In the event we are unable to recruit a Site Champion, all Site Champion communications will come from the study team.
- Once Site Champions have obtained approval from the MCD, each site will be randomized to the **Or** or **Sc** arm. The Data Manager will work with our Consultant, [name] on randomizing sites.

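### Eligibility at trial sites is listed after randomization, judged without described masking and re-checked differently by arm, so the primary-outcome denominator could depend on arm if the delivery list is also the analysis list

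*Protocol*

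**What the plan says.** **Allocation comes first.** Under Trial Site Selection, "We will randomize 4 VA facilities with high rates of low-value ADT use". Under Trial Site Recruitment & Randomization, "Once Site Champions have obtained approval from the MCD, each site will be randomized to the" order-check (Or) or script (Sc) arm. The list of potentially eligible patients follows, under Patient Dashboard in CPRS: "Once a site is randomized, the Data Manager will run a new data pull for that site". That sentence concerns the trial, because pilot sites are not randomized.

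**Review needs judgement.** Chart Reviews states: "Clinic visits identified during chart reviews or multi-disciplinary review as involving proper justification for ADT use will not be considered appropriate for ADT de-implementation". Doubtful bone metastases, intermittent ADT and other unclear cases go to the study team's weekly meeting.

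**The same staff deliver.** In Or, study staff place a "health factor in the EMR of patients whose clinic visits study staff have confirmed to be targets for ADT de-implementation". In Sc, study staff write the progress note and assign it to the provider. The chart-review form records eligibility and the tool delivered in one outcome field.

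**Identification continues after launch.** For Or, once the order check is live: "We will enter health factors as we identify eligible patients". For Sc: "Study staff will screen the list of clinic visits throughout the implementation period". The Sc sentence stands under a pilot heading. It reaches the trial through Trial Or/Sc Implementation, which says trial procedures will resemble the pilot's, with refinements.

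**Outcome base.** The Data collection section takes outcomes from visits documented as low-value ADT at baseline, 3 and 6 months. The effectiveness row of Table 4 is built from low-value ADT candidates, orders placed and orders stopped.

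**The concern.** In a cluster trial, randomization protects the comparison of patients only if the patients are fixed independently of the arm. Here the decision on who counts as a low-value ADT case comes after the arm is known and is partly a matter of judgement. It also runs through different steps in the two arms. If those steps feed the analysis set, one arm can shed or gain patients whose chance of stopping differs from the rest. The apparent stop rate then moves although neither tool did anything. With four sites, such a difference cannot be expected to average out.

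**Working it through.** The protocol gives no stop rate, number of patients per site, power or effect size for the trial, so there is no planned figure to reproduce. The check has two parts.

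**1. The pathways side by side**

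| Step | Or | Sc | Control sites |
|---|---|---|---|
| List pulled | After randomization | After randomization | Not randomized |
| Identification after launch | Yes (Or Intervention section) | Yes (pilot section, carried over to the trial) | First review does not look past the matched launch date (Trial Data Collection) |
| Re-check at delivery | Software tests latest PSA when ADT is ordered | Staff check PSA and all exclusions before each note | None needed |
| Result of failing | Order check does not fire; no eligibility recoding described | Marked not eligible, all three inclusions set to no | Not applicable |
| Visits without the tool | None by visit type; any listed ADT order for a flagged patient can trigger | Injection-only visits get no note | Not applicable |

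The Sc re-check steps sit in the CPRS instructions for Sc, which name two trial sites, Columbia and Phoenix, so they are not only pilot text. The removals described for Or concern providers who opt out and the close of the intervention, not a patient failing a re-check. An eligibility review tied to a launch date is described for control sites only.

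**2. What an arm-specific removal could do**

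All inputs are assumptions. Let *s* be the true stop rate in both arms (no effect), *f* the share removed after launch in one arm only, and *g* the stop rate among those removed.

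Apparent rate = (s − f·g)/(1 − f)

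Shift = (s − f·g)/(1 − f) − s = f(s − g)/(1 − f)

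With s = 20%:

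| f | g = 0 | g = 10% |
|---|---|---|
| 5% | 0.20/0.95 = 21.1%, +1.1 points | 0.195/0.95 = 20.5%, +0.5 |
| 10% | 0.20/0.90 = 22.2%, +2.2 | 0.19/0.90 = 21.1%, +1.1 |
| 20% | 0.20/0.80 = 25.0%, +5.0 | 0.18/0.80 = 22.5%, +2.5 |

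Over s = 10-30%, f = 5-20% and g from 0 to s/2, the extremes are:

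- Smallest (s = 10%, f = 5%, g = 5%): 0.0975/0.95 = 10.26%, about +0.3 points.
- Largest (s = 30%, f = 20%, g = 0): 0.30/0.80 = 37.5%, or +7.5 points.

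The sign is that of s − g. If those removed would have stopped more often than the rest, the shift is negative; if equally often, it is zero. If everyone on a fixed list is analysed, f = 0 and this artificial shift is zero in every scenario.

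**The case against.** The strongest reply is that these sections govern who receives the tool and do not define an analysis set. Trial Data Collection leaves the outcome analysis plan to be developed, and the SAP is not available here. That stands. A reader might infer that patients recoded as not eligible leave the primary analysis, but the protocol does not say so.

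The room for judgement is also limited. One set of written criteria applies to both arms, covering PSA, PSA doubling time, treatment history and injection within 14 months. A validated language-processing tool screens for metastases, and the cohort draws on a common 2020-2022 window. Unclear cases go to review by a urologic oncologist, a medical oncologist and a radiation oncologist rather than resting only with the staff who place the tool. No patients are recruited, so selection through consent does not arise. All this narrows the problem. It does not mask the calls that remain, and it does not make the Or and Sc re-checks alike. That asymmetry needs no assumption of reviewer bias.

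The pilot text for Or does pull and review a cohort before launch. The live Or instructions nevertheless add patients as they are found.

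Finally, review before allocation is too late for some sites. The protocol version dated 10/04/2023 already names Columbia and Phoenix as Sc sites, with a note-assignment instruction starting 8/10. This limits the remedy, not the point.

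**Conclusion.** The point holds as a conditional risk. The list is pulled after allocation, no masking of reviewers is described, identification continues after launch, and re-check and recoding differ by arm. If the delivery list is also the analysis list, the cohorts and the primary-outcome denominator can depend on arm.

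A reader might go further and conclude that the arms are already unbalanced or that a bias of known size and direction exists. The protocol supports neither. It reports no arm-specific counts and no stop rates. The range of about +0.3 to +7.5 points rests wholly on the assumed 10-30% stop rate and 5-20% removal in one arm, with those removed stopping at no more than half the overall rate. The shift could equally be negative or nil.

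The SAP could define the analysis population, but it could not retrospectively mask judgements made with the arm known. The order of pull, review and re-check belongs to protocol procedure and should be settled there.

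**What to change.** For the primary analysis, define each site's cohort at one index date: intervention launch at Or and Sc sites, and the matched launch date at control sites, as Trial Data Collection already implies. Use only records dated before that date, with the same criteria at all sites.

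- Analyse everyone on the list, whether or not an order check or note was delivered.
- Let later PSA and eligibility re-checks decide delivery only, and state that recoding does not remove a patient from the denominator.
- Report patients identified after the index date separately.
- At sites not yet allocated, finish the pull and review before randomization. Director approval already precedes allocation, and Chart Reviews allows Capri or JLV where local access is pending.
- At sites already allocated, rebuild the list from pre-launch records and have questionable cases re-judged from extracts that do not show the arm.

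The cost is some repeat review and possibly a short wait before allocation at any remaining site, which matters because the Timeline section ends funding on 12/31/2023. A few patients who become ineligible after launch stay in the denominator and slightly dilute the effect. The data sources and reviewers are already planned.

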- Once the CROC has been switched to live mode, study staff will place a "Living Well ADT" health factor in the EMR of patients whose clinic visits study staff have confirmed to be targets for ADT de-implementation. We will enter health factors as we identify eligible patients. This health factor combined with a low PSA level (most recent PSA < 2ng/mL) will trigger the ADT Order Check Attestation Intervention (**Or**) when the provider places an order for ADT (Lupron, Eligard, Viadur, Goserilin, and Zolodex).
- Providers may override the CROC by entering a number from the order check text that corresponds to the reason they are overriding the order check. Providers are also able to enter text if a numbered reason is not listed.
- If providers opt-out after the health factor was placed for one of their patients, study staff will remove the health factor in CPRS. For a provider who opts-out, the Study Data Manager will run a query in our Access tracking database to pull a list of his/her patients. The Study Team will not place a health factor in the EMR of patients whose provider has opted out.
- Study staff will do periodic quality control checks to ensure the intervention is working as expected and work with the site CAC's to make adjustments as necessary.
- Appropriate use of the indication will be tracked for fidelity. We will track comments entered by providers to override order checks. The Study Data Manager will periodically pull comments from order checks (there are data tables for order checks that contain text for open field that are stored in CDW).
 - Using a combination of progress notes and other CPRS data, study staff will check to determine whether the patient received the injection.
- Deimplementing Or – study staff will remove HFs for intervention patients. We'll ask site to remove study HF from their CPRS.

CPRS INSTRUCTIONS FOR OR INTERVENTION

OPENING CPRS

- Go to "VA Shortcuts" (star icon on desktop)
- Select "CPRS _Launcher" (rocket icon)
- Select: VISN 03 or VISN 22
- Select site: Ex - Manhattan, NY
- Launch CPRS button

PLACING A HEALTH FACTOR

While in a patient record in CPRS:

- Click on the "Notes" tab (bottom of screen)
- Select (highlight) the note that makes most sense to you to add the health factor. **Ideally this will be the last progress note by the provider who prescribes this patient ADT.** Note: it shouldn't hurt anything to add this to another encounter if the last progress note by the provider who prescribes ADT isn't an option – the only consequence of this health factor is triggering our order check while the order check is live at the site.
- Click on the "Encounter" button (far right over tabs).
- Click "Edit Note Encounter" button in the "Select and Encounter to Edit" pop-up menu.
- Select "Health Factors" tab at the top of the Encounter Form pop-up menu.
- Select "Other Health Factor..." button in the middle left side of the pop-up menu.
- Enter "Living Well ADT" (or some portion of this) into the category box in the "Other Health Factors" pop-up menu.
- Select "Living Well ADT" by clicking on it in the "Category:" menu so that it is highlighted.
- Click "OK." The "Living Well ADT" health factor should show up under "Selected Health Factors."
- Click "OK" again until pop-ups close and the progress note screen is again fully visible.
- You can see in the bottom box under the progress note text "Health Factors: LIVING WELL ADT" to verify the health factor was added to the encounter.

DOCUMENTING PLACEMENT OF HEALTH FACTOR – EXCEL SPREADSHEET

- Update column "X" with date and full name of the encounter you added health factor.
 - Ex: "Yes – Oct, 13, 2022 UROLOGY CLINIC NOTE, GI/UROLOGY..."
- Update column "Y" with date health factor was added.
- Update column "AA" to indicate whether the dashboard was updated.

REMOVING HEALTH FACTORS IN CPRS

- Click on the "Notes" tab (bottom of screen)
- Select (highlight) the note where you added the health factor.
- Click on the "Encounter" button (far right over tabs).
- Click "Edit Note Encounter" button in the "Select and Encounter to Edit" pop-up menu.
- Select "Health Factors" tab at the top of the Encounter Form pop-up menu.
- Find and select the "Living Well ADT" health factor in "Selected Health Factors."
- Click "Remove."
- You should no longer see in the bottom box under the progress note text "Health Factors: LIVING WELL ADT" to verify the health factor was removed from the encounter.

DOCUMENTING PLACEMENT OF HEALTH FACTOR – DASHBOARD - TBD

SCREENSHOT OF CPRS ORDER CHECK

Order Checking

(1 of 2) Duplicate Therapy: Order(s) exist for {LEUPROLIDE (ELIGARD) 22.5MG(3 MONTH) LA INJ [PENDING]} in the same therapeutic categor(ies): LHrH(GNrH) Agonist Analog Pituitary Suppressants, Precocious Puberty Agents

(2 of 2) ADT Advisory - Living Well
This patient has a PSA < 2 and does not appear to have metastatic prostate cancer based on multidisciplinary review.

For this clinical scenario, where the harms of ADT likely outweigh the benefits, NCCN (tinyurl.com/2p9f5w8r) and AUA (tinyurl.com/4ueptrtd) guidelines recommend either transitioning to intermittent ADT or discontinuation of ADT.

Instead of ADT now, consider patient reassurance with return visit in 3 months for a PSA test and symptom assessment.

Please enter reasons for overriding order checks as free text or a number from the list below:

- 10. Provider recommendation: Local Symptoms OR Asymptomatic, high-risk/very high-risk, N0/M0 with less than 5 year life expectancy.
- 20. Provider recommendation: Rapidly rising PSA/short PSA-DT (<10 months)
- 30. Provider recommendation: Metastatic or presumed metastatic disease
- 40. Provider recommendation: Castration resistant prostate cancer
- 50. Patient Preference/anxiety (consider reassurance with return visit in 3 months for PSA check)

Accept Order Cancel Order Drug Interaction Monograph

PROVIDER SCRIPT (Sc) INTERVENTION

- The pilot work will be used to refine the Provider Script Intervention for use in the cRCT, as needed.
- The purpose of the script is to enable providers to:
 - Improve interpersonal skills
 - Increase confidence in the evidence base and communication surrounding low-value care
- It is up to the discretion of the provider whether/how to incorporate the script into the clinic visit discussion.

PROGRESS NOTE

- We will work with [name] ([contact]), or another, AAVA CAC, to develop the progress note template. We will also create an instruction guide for CACs at other sites to upload the note template file in CPRS.
- [name], or another AAVA CAC will send the note template via VISTA email to local CACs with directions to install. In the event [name] is not available, [name] ([contact]), or [name] ([contact]) can send the VISTA file if we provide them with the local CAC's VISTA email.
- This is the exact entry for the reminder dialog they would need unless we make any updates to it between now and then.

+Item	Entry	Source	Date Packed
181	LIVING WELL ADT FILES - DEC 2022	[name]	12/13/2022@10:12

- Study staff will enter a CPRS progress note approximately one business day prior to a target low-value ADT clinic visit. Notes will not be assigned for ADT injection-only visits. The note includes talking points for the provider to help with a discussion with the Veteran.
 - The note can be edited and signed by the provider, giving a quick and simple way to document the discussion. The progress note will prompt providers to indicate whether patient prefers to continue or discontinue ADT.
- The progress note will include links to the clinic handout which will be posted on CCMR's external website (outside VA firewall).
- Providers may modify, ignore, or delete the progress note.
- Appropriate use of the indication will be tracked for fidelity. We will track how many notes are placed. We will also be able to run a report of all signed and unsigned progress notes.
- At the end of the intervention period, Ann Arbor CAC's will delete/remove all unsigned progress notes. Unsigned notes will need to be reassigned at the end of the study. [name], or another AAVA CAC will run a report of unsigned notes by our note title for Ann Arbor. The CAC will change the note author back to a member of the study team, which we can then remove from CPRS. We will ask the Data Manager to reassign the note in CDW for other sites or ask the site CAC if necessary.
 - If providers delete an unsigned note, it's unlikely to appear in a TIU progress note report.

CLINIC HANDOUT

- The clinic handout will be tailored to each individual facility, e.g., with site name (Appendix V).
- Prior to each site's scheduled IES, study staff will provide clinic handouts to the clinic point person identified by the Site Champion (the clinic point person may also be the Site Champion). We may use one or more of the following approaches:
 - By mail: hardcopies of the handout will be mailed to the clinic point person (as requested). Each clinic will receive 50 copies of the handout.
 - By email: copies of the handout will be emailed to clinic point person (this may happen when we send Site Champions the email templates or in a separate email). Each clinic will be instructed to print 50 copies of the handout.
 - By website: a copy of the handout will be accessible on CCMR's website (outside the VA firewall). A link to the website will be included in the progress note.
- If requested by sites, the study will provide supplies to sites to display the clinic handouts. Study staff will check in to ensure handouts were received and are being displayed and/or made accessible to providers and to address any issues that come up.
- It is up to the discretion of the provider whether/how to incorporate the handout into the clinic visit discussion.

CPRS INSTRUCTIONS FOR Sc INTERVENTION

ASSIGNING A PROGRESS NOTE

1. Open TWO files:
 - a. CPRS
 - b. *Database
 - i. Note: Starting 8/10, [name] will assign progress notes for Columbia and Phoenix patients.
 - ii. Note: Starting 8/14, [name] will update the appointment list for eligible patients each week (on Mondays). The database will list dates of upcoming appointments in chronological order.
2. While in a patient record in CPRS:
 - a. Confirm patient name and SSN match what's in the database (you're just confirming that you're looking at the correct person in CPRS).
 - b. In CPRS, go to "Appointments" in the "Cover Sheet" to confirm that the appointment listed in the database matches what's listed in CPRS.
 - i. If the date and/or name of an upcoming appointment in CPRS is different than what is in the database, update the "Visit datetime" and "Clinic" name in the database.
- c. In CPRS, confirm the MOST RECENT PSA has not increased beyond 2ng/ml.
 - i. **IF** the patient has a PSA <2ng/ml, skip to Step 2d.
 - ii. **IF** the patient has a PSA >2ng/ml, go back to the database, open the form for the patient, click "View/Edit Chart Reviews" and edit the Patient Chart Review page:
 - 1) HF/Note Comments – add reason for not assigning progress note (i.e., why patient is ineligible) – comment should read as: "Prior to assigning note, it was confirmed the patient's most recent PSA on [DATE] was [PSA value]."
 - 2) Not Elig. At Visit box – check this box
 - 3) Exclusions – select "Yes" next to "Current PSA >2 or rapidly rising"
 - 4) Inclusions – mark all three inclusions "No"
 - 5) Notes – add reason for not assigning progress note (yes, you will repeat step 2.c.i.1) – comment should read as: "Prior to assigning note, it was confirmed the patient's most recent PSA on [DATE] was [PSA value]."
 - 6) Outcomes – mark "Not Eligible"
 - 7) Click "Save"
 - iii. Note: If the patient is ineligible for another reason (i.e., patient is deceased, provider opted out, etc.) follow steps 1)-7) to update this page. The details should be relevant to the specific situation.
- d. In CPRS, confirm all other eligibility criteria. The patient must NOT meet any of the exclusion criteria prior to assigning a note.
- e. In CPRS, click on the "Notes" tab (bottom of screen).
- f. In CPRS, click on the "New Note" tab. *Location for Current Activities* dialog box will open.
- g. In CPRS, click on the "New Visit" tab (far right over tabs).
 - i. [PILOT] For Ann Arbor, enter "AA GM-LETTER-X" to attach the note
 - ii. [RCT] Enter the following to attach the note:
 - 1) Columbia – **WJB RESEARCH NOTES**
 - 2) Phoenix – **ADMINISTRATIVE CONTACT**

Version 6, 10/04/2023

Page 38 of 88

- h. Time of visit should be set to "Now" (do **NOT** check the "Historical Visit" button).
- i. Click "OK."
- j. ****In Progress Note Properties box, enter "ADVISORY-ADT FOR LOCALIZED/NON-METASTATIC PROSTATE CANCER".** Once you see the note title in the menu, click to highlight it, and then click "OK."
- k. *Reminder Dialog Template: Advisory - ADT for Localized/Non-Metastatic Prostate Cancer* box will open. Click "Finish."
- l. *Primary Encounter Provider* box may open. Enter the name of the provider. Once you see the provider's name in the menu, click to highlight it, and then click "OK."
- m. Tailor the note for each patient:
 - i. Delete one of the options in the first sentence "based on multidisciplinary review..." prior to assigning the note (primary ADT or BCR). Refer to the database to see the patient's eligibility.
- n. In the event you need to manually enter PSA lab values and ADT injection information, please include data for the **three most recent PSA labs and ADT injections within the last year.**
 - i. The best place to find this information is in the progress notes for an ADT injection appointment (they *may* include "Uro" or "Onc" in the title – do not assume information about an ADT injection is not available just because a note doesn't include "Uro" or "Onc" in the title). You can also find information about ADT injections in the progress notes and in the Meds tab.

UROLOGY CLINIC NOTE, WJB SURG GU PROV 2 CL MD, ← ADT discussion
 UROLOGY INJECTIONS NOTE, WJB SURG GU NURSING, ← ADT injection only appointment

- ii. If the patient doesn't have three ADT injections in the last year, just add the two most recent injections.
- iii. Refer to the progress note template to see what information should be included and how the section should be formatted.
 - 1) At a minimum, the name of the medication, dosage, location of injection and date of administration should be included. If you can include additional information about the medication (expiration date and Lot #), include that in the note as well. If that information is not available, delete the Exp. Date/Lot# titles.
 - 2) Remove excess space between paragraphs. Make sure asterisks (*** line up at the bottom of the note.
- o. Click "Change..." box at top right of screen.
- p. Click on arrow at right of "Author:" drop down menu in *Progress Note Properties* note and select the provider who makes decisions about ADT for this patient.
- q. Click "OK"

3. After assigning the note, update the Chart Review form in the database for the patient. To do this, open the form for the patient, click "View/Edit Chart Reviews" and edit the Patient Chart Review page.

- a. Add date you assigned progress note to "Date HF/Note Assigned."
- b. Add comment in the "HF Note Comments" AND "Notes" fields. The "Notes" field is at the bottom of the page.
 - i. The comment for COLUMBIA should read: "Progress note assigned to Dr. [name] on [date] by [your initials] to WJB Research Notes encounter."
 - ii. The comment for PHOENIX should read: "Progress note assigned to Dr. [name] on [date] by [your initials] to [name of Phoenix encounter TBD] encounter."
- c. Select "Eligible – Note Assigned" under "Outcomes."
- d. Click "Save" then close out of the screen.

Patient Chart Review Page (Database)

Prostate Cancer Dx Date:	Patient ID: 505	Provider Rx'd ADT:	Most Recent ADT Injection:	Date HF/note assigned:	Date HF/note removed:	HF Note Comments:																																
Screen Date Time  Couldn't reach pt  Not Elig. at Visit Eligibility Reason Primary ADT (no definitive tx)																																						
Exclusions 
 
 Provider Opted Out	Yes	No	
 
 Deceased	Yes	No	
 
 mPC-including local nodes	Yes	Unclear	No	
 
 VA ADT injections ongoing	No	IADT	CC (decisions made by community care)	Unclear	Yes	
 
 Current adjuvant ADT	Yes, having/had XRT	Yes, plan for XRT	Unclear	No	
 
 CRPC	Yes	No	
 
 Current PSA > 2 or rapidly rising	Yes	No	
 
 Other	Other (add comment on note section below)	Other Specify	
 
							Provider Opted Out	Yes	No	Deceased	Yes	No	mPC-including local nodes	Yes	Unclear	No	VA ADT injections ongoing	No	IADT	CC (decisions made by community care)	Unclear	Yes	Current adjuvant ADT	Yes, having/had XRT	Yes, plan for XRT	Unclear	No	CRPC	Yes	No	Current PSA > 2 or rapidly rising	Yes	No	Other	Other (add comment on note section below)			Other Specify
Provider Opted Out	Yes	No																																				
Deceased	Yes	No																																				
mPC-including local nodes	Yes	Unclear	No																																			
VA ADT injections ongoing	No	IADT	CC (decisions made by community care)	Unclear	Yes																																	
Current adjuvant ADT	Yes, having/had XRT	Yes, plan for XRT	Unclear	No																																		
CRPC	Yes	No																																				
Current PSA > 2 or rapidly rising	Yes	No																																				
Other	Other (add comment on note section below)			Other Specify																																		
Inclusions 
 
 Definitive Tx	Any	Unclear	No	
 
 ADT for BRPC	Yes	No	
 
 No PSA recurrence and >3yrs adj/adj ADT	Yes	No	
 
							Definitive Tx	Any	Unclear	No	ADT for BRPC	Yes	No	No PSA recurrence and >3yrs adj/adj ADT	Yes	No																						
Definitive Tx	Any	Unclear	No																																			
ADT for BRPC	Yes	No																																				
No PSA recurrence and >3yrs adj/adj ADT	Yes	No																																				
Next ADT Visit	Notes:																																					
Outcomes  Not Eligible  Eligible - added HF  Eligible - assigned note  Eligible - no intervention																																						
																																						

Important Notes:

1. *Check the database every morning to determine if a progress note needs to be assigned for an appointment the following day.
2. If a note is mistakenly assigned to the wrong provider, or for a patient who is ineligible, notify [name] and [name] immediately.
3. Provider transitions – If you need to assign notes for eligible patients whose ADT prescriber is no longer in CPRS (and there's no other indication of who patients will be meeting with for their upcoming appointment), ask Site Champion if they wish to have those notes assigned to them or transfer them to another provider on our list.
4. **When selecting note from CPRS "Progress Note Properties" box, you will see two notes with the same title in the list. It's not a duplicate note, it's a quirk of CPRS that displays the note twice. It has to do with how more titles are created and that note titles can have a print name that is different. Whenever we create a note title, it creates 2 lines in CPRS that make it look that there are two titles but there's only the one. You may select either note with our title.
5. Do not assign notes for ADT injection-only visits.
6. Once you have assigned this unsigned progress note to an author that isn't yourself, only that person will see this unsigned progress note in CPRS. Notes signed by the author will be visible to everyone in CPRS.
7. If you try to select a new patient or exit CPRS with an unsigned note, it will prompt you to see if you want to sign it or proceed and delete it.

8. If you accidentally select "Add Chart Review" in the patient form in the database, thereby creating a new duplicate record, just go into the table and find the row that's the duplicate and delete it.

CPRS PROVIDER PROGRESS NOTE TEMPLATE

Available in AAVA CPRS: Shared template>> ZZ considered>>[name] test>>prostate study note

Mock data (dates, results, etc.) shown in note

Original Template Version

Advisory: ADT for Localized/Non-Metastatic Prostate Cancer

Based on multidisciplinary review, this patient appears to be on ADT [as primary therapy for] or [as treatment for biochemically recurrent] prostate cancer.

Most recent PSA values:

